### **10.1.2 Adverse Events Leading to Withdrawal**

A summary of incidence rates (frequencies and percentages) of AEs leading to withdrawal, by treatment group, System Organ Class, and Preferred Terms, will be prepared for the Safety Population. No statistical tests will be performed.

A data listing of AEs leading to withdrawal will also be provided, displaying details of the event(s) captured on the CRF.

### **10.1.3 Serious Adverse Events**

Serious adverse events reconciliation will be performed by Data Management, Clinical Research, and Golden Drug Safety and Pharmacovigilance via data listings.

A summary of incidence rates (frequencies and percentages) of SAEs by treatment group, System Organ Class, and Preferred Term will be prepared for the Safety Population. No statistical tests will be performed.

A data listing of SAEs will also be provided, displaying details of the event(s) captured on the CRF. Serious adverse event narratives will be provided for the CSR by the Golden Drug Safety and Pharmacovigilance Department.

Protocol: GHLIP-2-001

Study Sponsor: Golden Biotechnology Corporation

### 10.1.4 Deaths

If any patients die during the study, relevant information will be supplied in a data listing, and appropriate SAE narratives.

### 10.1.5 Other AE Assessments

No other assessments or analysis are planned.

## 10.2 Clinical Laboratory Evaluations

Descriptive summaries (mean, SD, median, minimum, and maximum for each group with related 95% confidence interval.) of changes from baseline will be presented for clinical laboratory values by treatment for the Safety Population.

The number of patients with clinical laboratory values below, within, or above normal ranges, pre-procedure versus post-procedure will be tabulated for each test, for the Safety Population by treatment group. Pre- and post-procedure values will also be presented with an analysis of mean changes from baseline. Laboratory assessment results will be classified to normal or abnormal, and will be tabulated with related frequency and percentages. The shift tables of laboratory results will also be provided.

Laboratory values that are outside the normal range will also be flagged in the data listings, along with corresponding normal ranges. Any out-of-range values that are identified by the investigator as being clinically significant will also be shown in a data listing.

## 10.3 Other Safety Measures

- Vital Signs

**Protocol: GHLIP-2-001**

**Study Sponsor: Golden Biotechnology Corporation**

Descriptive statistics of actual, values and changes from baseline will be calculated for heart rate, Blood pressure, body temperature, weight, waist circumference, hip circumference and body fat.

- 12-Lead ECG

Individual ECG values will be listed and summarized by descriptive analysis. Comparisons between baseline ECG and post-screening ECGs result will also be evaluated.

- Physical Examinations

Results of physical examination for abnormality will be listed.

## **11 REPORTING CONVENTIONS**

The following reporting conventions will be adopted for the SAP. These conventions will enhance the review process and help to standardize presentation with common notations.

### **11.1 General Reporting Conventions**

All tables, figure, and data listings will have the name of the program and a date/time stamp on the bottom of each output and will be presented in Landscape Orientation. Unless presented as part of the text in a CSR.

All titles will be left justified and top of the page, and all footnotes will be left justified and the bottom of a page. Missing values for both numeric and character variables will be presented as blanks or “.” in a table or data listing.

All data values will be presented as MM/DD/YYYY (e.g., 08/29/2001) format. A four-digit year is preferred for all dates.

Protocol: GHLIP-2-001

Study Sponsor: Golden Biotechnology Corporation

## 11.2 Population/Statistic Summary Conventions

Population(s) represented on the tables or data listings will be clearly identified in the last title of the Table as "Population: [name of population]" and will be identical in name to that identified in the protocol or SAP.

Consistent terminology will be used to define and identify a population. Common nomenclature may include (a) ITT, (b) PP or Per-Protocol, and (c) Safety.

Population sizes may be presented for each treatment or dosing category as totals in the column header as (N=xxxx), where appropriate.

All population summaries for categorical variables will include categories that the patients had a response in these categories.

All population summaries for continuous variables will include: N, mean, SD, minimum, and maximum. Other summaries (e.g. median, quartiles, 5%, 95% intervals, CV or %CV) may be used as appropriate. All percentages are rounded and reported to two decimal points.

Population summaries that include p-values will report the p-value to three decimal places with a leading zero (0.001). All p-values reported on default output from statistical software (i.e., SAS® Software) may be reported at the default level of precision. P-values <0.001 should be reported as <0.001 not 0.000.

## 12 SUMMARY OF CHANGES TO THE PROTOCOL

No change in non-statistical and statistical analysis to the protocol.

Protocol: GHLIP-2-001

Study Sponsor: Golden Biotechnology Corporation

## 14 APPENDIX

### 14.1 Mock-up Tables

- Statistical Table
- Data Listing

Protocol: CYBBV1302

Study Sponsor: Chuang-Yi Biotech Corp., Ltd.

## Statistical Table

Page 1 (LAST PAGE)

Table 14.1.2.1 Summary of Demographic and Baseline Characteristics (Safety Population)

Characteristics	Antroquinonol 50 mg (N= )	Antroquinonol 100 mg (N= )	Antroquinonol 150 mg (N= )	Placebo (N= )	P-Value
-----------------	------------------------------	-------------------------------	-------------------------------	------------------	---------

Age &  
NUMBER  
MEAN  
S.D.  
RANGE  
95% C.I.

Gender #  
MALE  
FEMALE

Race #  
ASIAN  
TAIWAN INDIGENOUS  
CAUCASIAN  
BLACK  
OTHER

=====  
Program name: Antro\_T\_DEMO.sas   Programmer:  
RANGE: (Minimun, Maximum); S.D.: Standard Deviation; CI: 95% Confidence Interval  
&: P-value was conducted by T-test/Kruskal-Wallis test for Continuous Variables  
#: P-value was conducted by Chi-square/Fisher's exact test for Categorical Variables

## Data Listing

Listing 16.2.1.1 --- Subject Early Termination

Page 1 of 2

Site No.	Screening No.	Subject No.	Did Subject Complete the Study?	What Was the Primary Reason for Early Termination/Withdrawal?
----------	---------------	-------------	------------------------------------	--

=====  
Site No.: 1=National Taiwan University Hospital, 2=China Medical University Hospital, 3=National Cheng Kung University Hospital,  
3=National Cheng Kung University Hospital, 4=Taipei Veterans General Hospital, 5=Far Eastern Memorial Hospital, 6=Chang Gung  
Memorial Hospital, Linkou branch

=====  
=====

## 14.1 Planned Tables

The contents of Statistical analysis tables and data listing follow ICH E3 Guidelines for tables, figures and graphs.

### Statistical Tables

#### 14.1 Demographic Data

Table 14.1.1.1 Summary of Subject Disposition by Treatment Group

Table 14.1.1.2 Primary Reason for Discontinuation

Table 14.1.2.1 Summary of Demographic and Baseline Characteristics (Safety Population)

#### 14.2 Efficacy Data

Table 14.2.1.1 Primary Endpoint: Percentage change of TG after 12 Weeks (ITT)

Table 14.2.1.2 Primary Endpoint: Percentage change of TG after 12 Weeks (PP)

Table 14.2.2.1 Secondary Endpoint: Percentage change of TC, HDL-C, LDL-C, and LDL/HDL after 12 Weeks (ITT)

Table 14.2.2.2 Secondary Endpoint: Percentage Change of TC, HDL-C, LDL-C, and LDL/HDL after 12 Weeks (PP)

Table 14.2.3.1 Secondary Endpoint: Percentage Change of E/E', baPWV, ABI, and HU after 12 Weeks (ITT)

Table 14.2.3.2 Secondary Endpoint: Percentage Change of E/E', baPWV, ABI, and HU after 12 Weeks (PP)

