7.5. Laboratory Evaluations

7.5.1 Clinical laboratory evaluations

Laboratory tests (including hematology, biochemistry, and urinalysis) will be scheduled as below. The examination items are included in **Table 7- 1**.

Lipid Profile: Blood samples to assess total cholesterol, triglycerides, HDL-C, LDL-C, LDL/HDL ratio will be obtained from visit 1 to visit 5.

Hematology: Blood samples to assess WBC, RBC, Hb, Hct, RDW, platelet, MCV, MCH, MCHC, neutrophil-band and segment, lymphocyte, monocyte, eosinophil, basophil will be obtained at visit 2 and visit 5.

Serum Biochemistry: Blood samples to assess AST, ALT, CPK, BUN and serum creatinine will be obtained from visit 2 to visit 5, albumin, total bilirubin, direct bilirubin, ALP, total protein will be obtained at visit 2 and visit 5. At screening visit, serum creatinine shall be run for estimating glomerular filtration rate (GFR).

Urinalysis: Assessments of urine pH, protein, glucose, ketone, blood, urobilinogen, bilirubin, nitrite, leukocyte and clinical microscopy will be tested at visit 2 and visit 5.

Pregnancy Test: Urine HCG test will be performed at visit 1.

12-lead ECG: ECG will be performed in accordance with the standard procedures at the site at visit 2 and visit 5.

baPWV and ABI measurement: baPWV is used to assess arterial stiffness and will be

obtained using VP 1000 or VP 1000 plus (Omron) at visit 2 and visit 5/early termination visit. ABI is a surrogate marker of atherosclerosis and will be obtained using the same device at visit 2 and visit 5/early termination visit.

Echocardiography: Values for S', E', and A' will be measured and averaged over three consecutive cardiac cycles. A composite mean for each of these parameters is then formed by taking the average of the values from the septal, lateral, and inferior wall. The ratio of the transmitral Doppler E wave velocity and the composite mean of E' will then be used to calculate the E/E' ratio. E/E' ratio will be obtained at visit 2 and visit 5.

CT scan of the liver: Each participant will undergo non-enhanced liver computed tomography (CT) scans at visit 2. The Hounsfield Unit (HU) attenuation of liver on CT scans will be utilized for determination of fatty liver (L/S ratio <1.0 and liver attenuation <40HU). Subjects who are confirmed with fatty liver will undergo liver CT scans again at visit 5.

Table 7- 1 Laboratory tests planned to be performed

Hematology	Biochemistry	Urinalysis	Others

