**Protocol: GHLIP-2-001**

**Study Sponsor: Golden Biotechnology Corporation**

### **3.2.2 Secondary Endpoints**

1. The effect of Antroquinonol in comparison with placebo on the percentage change in total cholesterol, HDL-C, LDL-C and HDL/LDL ratio from baseline after 12 weeks of treatment.
2. The effect of Antroquinonol on the ratio of mitral velocity to early diastolic velocity of the mitral annulus (E/E' ratio) with tissue Doppler imaging and baPWV and ABI via a non-invasive arterial stiffness measurement.
3. The effect of Antroquinonol on the fatty liver prognostic with CT scan.

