**Protocol: GHLIP-2-001**

**Study Sponsor: Golden Biotechnology Corporation**

Concomitant Therapy	X	X	X	X	X	X
Adverse Event		X	X	X	X	X

\* A wash-out period of 2 weeks will not be applied to patients prior treated with medication which does not affect serum lipid level.

1. Vital signs: pulse rate, body temperature, respiratory rate, and blood pressure (including systolic blood pressure (SBP) and diastolic blood pressure (DBP)).
2. Including height, weight, waist circumference, and BMI (calculated by kg/m^2)
3. Subjects who meet the eligibility criteria will be randomized into treatment arms. If the eligibility is confirmed and a wash-out period is not needed for the subject, based on investigator's judgements the blood test required at V2 can be replaced by the data obtained 14 days before V2.
4. Serum lipids: total cholesterol, triglycerides, HDL-C, LDL-C, LDL/HDL ratio. Serum lipid results obtained 3 days prior to V1 is acceptable.
5. Doppler color flow mapping, and CT scan of the liver. CT scan will not be scheduled at visit 5 on subjects without fatty liver. Results of Doppler color flow mapping and CT scan of the liver obtained between V1 and V2 are acceptable.
6. hsCRP, IL-1, IL-6, and TNF-alpha.
7. WBC, RBC, Hb, Hct, RDW, platelet, MCV, MCH, MCHC, neutrophil-band and segment, lymphocyte, monocyte, eosinophil, and basophil.
8. Biochemical exam: AST, ALT, CPK, BUN and serum creatinine: visit 2 to visit 6; albumin, total bilirubin, direct bilirubin, ALP, total protein: V2, V5 and V6. At screening visit, serum creatinine shall be run for estimating glomerular filtration rate (GFR) and data obtained 3 days prior to V1 is acceptable.
9. Urinary exam: routine urine test (pH, protein, glucose, ketone, blood, urobilinogen, bilirubin, nitrite, leukocyte) and clinical microscopy.

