## 9.4 Secondary Endpoint Analyses

Analysis of other secondary efficacy endpoints (TC, HDL-C, LDL-C, and LDL/HDL ratio as well as the effect of Antroquinonol on E/E', baPWV and ABI and HU parameters) will be similar to the primary analysis of the primary endpoint by using ANCOVA model using baseline measurement as covariates, or using Kruskal-Wallis test when normal assumption is violated. Pairwise comparison will use two independent t-test or Wilcoxon rank-sum test, and performed significance level of 0.05 while statistical significance of ANCOVA or Kruskal-Wallis test treatment effect is achieved (Antroquinonol 50 mg vs. Placebo, Antroquinonol 100 mg vs. Placebo, Antroquinonol 150 mg vs. Placebo, Antroquinonol 100 mg vs. Antroquinonol 50 mg and Antroquinonol 150 mg vs. Antroquinonol 100 mg).

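### Liver HU is planned as percentage change, a scale that breaks down near and below 0 HU; absolute change is the better measure, and the size of the loss depends on baselines the documents do not give

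*SAP*

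**What the plan says.** - **Scale in the planned outputs.** SAP Appendix 14.2 lists Table 14.2.3.1, "Secondary Endpoint: Percentage Change of E/E', baPWV, ABI, and HU after 12 Weeks (ITT"), and Table 14.2.3.2 repeats it for the per-protocol population. No efficacy table shows absolute HU change.
- **Analysis.** SAP 9.4 says the analysis of the secondary endpoints, HU included, "will be similar to the primary analysis of the primary endpoint by using ANCOVA model using baseline measurement as covariates". If normality fails, a Kruskal-Wallis test takes its place. The primary analysis is on percentage change. Pairwise t-tests or Wilcoxon rank-sum tests follow a significant global test.
- **Endpoint text.** SAP 3.2.2 says only "The effect of Antroquinonol on the fatty liver prognostic with CT scan". Protocol 3.3 likewise gives percentage change for the lipids and no scale for the CT endpoint.
- **Formula.** SAP 7.6 defines percentage change for TG alone: Day 85 minus Day 1, divided by Day 1.
- **Who is measured.** Protocol 7.5.1 uses CT attenuation for "determination of fatty liver (L/S ratio <1.0 and liver attenuation <40HU") and adds that "Subjects who are confirmed with fatty liver will undergo liver CT scans again at visit 5". Footnote 5 to the flow chart in SAP 4.1.1 agrees: "CT scan will not be scheduled at visit 5 on subjects without fatty liver".

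Neither document sets a lower limit on baseline HU or a rule for a baseline at, near or below zero.

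**The concern.** Percentage change suits a quantity with a true zero that stays well away from it, such as TG at 150 to 500 mg/dL. HU is different. By definition of the unit its zero is water, so values can be zero or negative. Fatter liver reads lower. The rule for rescanning therefore picks out the patients with the smallest divisors, and nothing stops a divisor from being close to zero or negative.

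Three things follow. Equal improvements in HU receive unequal weight. Any patient with a baseline near zero can dominate an arm mean. A patient with a negative baseline who improves is scored as worse. At stake is the fatty-liver objective (Protocol 2.2, item 3): a real effect on attenuation could be missed or, in an unfavourable sample, shown with the wrong sign.

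**Working it through.** The plan gives no HU sample size, effect or SD, so there is no planned figure to reproduce.

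**1. The formula.** Apply 100 × (Visit 5 − Visit 2) / Visit 2 to a gain of 8 HU:

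- 35 to 43: 8/35 = +23%
- 4 to 12: 8/4 = +200%
- −4 to +4: 8/(−4) = −200%
- 0 to 8: undefined

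**2. A constructed arm.** Eight patients each gain 5 HU from baselines 30, 25, 20, 15, 10, 35, 28 and −2. Their percentage changes are 16.7, 20, 25, 33.3, 50, 14.3, 17.9 and −250. The mean is −9.1% although all eight improved; the median is +18.9%. With 32 in place of −2, the mean is +24.1%.

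**3. Power when the rank fallback is used.** Assumptions, none from the documents: 10 rescanned patients per arm, one active arm against placebo, true gain 8 HU, measurement SD 3, natural 12-week SD 4, measured baseline truncated at 40, two-sided 0.05.

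For absolute change, the SD of a patient's change is √(3² + 3² + 4²) = √34 = 5.83. The standard error of the difference is 5.83 × √(2/10) = 2.61, and 8/2.61 = 3.07. With 18 degrees of freedom this gives about 83% power, and simulation gives about 82 to 83%.

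For percentage change, the simulation uses a t-test, or a Wilcoxon test when Shapiro-Wilk rejects normality in either arm. The SAP names no normality test, so Shapiro-Wilk is also an assumption.

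| Baseline HU: mean, SD | Share of baselines below 0 | Power, percentage change |
|---|---|---|
| 33, 5 | about 0% | 79% |
| 30, 8 | about 0% | 76% |
| 25, 10 | 0.8% | 67% |
| 25, 12 | 2.5% | 59% |
| 20, 12 | 5.6% | 47% |

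With the t-test alone, the last four rows would be about 72, 51, 37 and 22%. In those four rows the arm means fall in the wrong order in about 1, 9, 14 and 22% of trials, but the arm medians in only about 0.7, 0.9, 1.2 and 1.9%.

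**4. Does the planned covariate help?** In SAP 9.3 baseline enters linearly, whereas the distortion goes as 1/baseline. A separate simulation (assumed +5 HU, SD of change 5, 12 per arm) used baseline-adjusted ANCOVA. Absolute change had about 63% power whatever the baseline. Percentage change had 63% (baseline 33, SD 5), 59% (30, 7), 50% (28, 10), 33% (25, 12) and 15% (20, 15). The covariate does not remove the problem.

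**The case against.** The strongest reply is that the plan has its own safeguard. Extreme ratios would fail a normality check, and SAP 9.4 then moves to rank tests. This carries real weight: in the worst scenario above, power is 47% with the fallback and 22% without it. It does not restore the 82 to 83% of absolute change, because ranking still puts improved patients with negative baselines at the bottom and still weights equal gains unequally.

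The second reply is that everything turns on baselines the documents do not report. This also stands. With baselines around 33 HU and SD 5, the comparison is 79% against 83%.

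Third, HU is also summarised in the safety-population tables (14.4.3.1 to 14.4.3.3) and listed in Listing 16.2.5.2, so an improvement would not be invisible. But no efficacy comparison of absolute change is planned.

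A reader might infer more than the documents support:

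- **That percentage change in HU is the defined endpoint.** It is not. The scale comes from two table titles and the cross-reference in SAP 9.4.
- **That the result is likely to be reversed.** Reversed arm means become appreciable only if a meaningful share of baselines lies near or below 0 HU. Nothing shows that such patients will be enrolled, and medians are rarely reversed.
- **That power falls to a quarter or less.** That is the t-test alone in the worst assumed scenario, without the SAP's rank fallback.

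**Conclusion.** The point holds as a weakness in the choice of scale. As the tables are planned, equal HU gains receive unequal values, which grow without limit near 0 and change sign below it. That follows from the formula, the definition of the unit and the selection rule, and does not depend on any assumption about patients.

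The size does depend on assumptions. Against about 82 to 83% power for absolute change, percentage change with the rank fallback runs from 79% (tight baselines well above zero) to 47% (mean 20, SD 12). These figures rest on an assumed effect, variability, number rescanned and normality test, and they leave out the four-arm global test that precedes the pairwise comparisons. They show direction and range and do not forecast this trial.

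This is a free improvement to one secondary endpoint. The TG primary analysis is not touched. The other measures in the same tables (E/E', baPWV, ABI) are positive quantities with a true zero, so the objection does not extend to them.

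**What to change.** In SAP 9.4, state that HU is analysed as absolute change, Visit 5 minus Visit 2 in HU, with baseline HU as covariate in the ANCOVA already planned. Retitle Tables 14.2.3.1 and 14.2.3.2 to match, or give HU its own pair of tables. Add the derivation to SAP 7.6. Keep percentage change for the lipids.

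Do this before database lock and unblinding, which SAP 6.2 already makes conditional on an approved SAP. It should be written in the SAP itself: SAP 7.6 allows further derived variables that are not primary or key secondary to be documented only in the programs, so an HU rule could otherwise be settled there.

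The cost is a few lines of text and the table titles. No new data are needed. Since Protocol 3.3 names no scale for the CT endpoint, the change contradicts no protocol text.

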### 14.3 Anthropometric measures

Table 14.3.1.1 Summary of Anthropometric measures (Safety Population)

Table 14.3.1.2 Summary of Mean Change from Baseline in Anthropometric measures (Safety Population)

### 14.4 Safety Data

Table 14.4.1.1 Summary of Vital Sign by Visit (Safety Population)

Table 14.4.1.2 Summary of Mean Change from Baseline in Vital Sign (Safety Population)

Table 14.4.2.1 Summary of of Physical Examinations (Normal/Abnormal) (Safety Population)

Table 14.4.2.2 Transition Table of Physical Examinations (Safety Population)

Table 14.4.3.1 Summary of baPWV, ABI, E/E', and HU (Safety Population)

Table 14.4.3.2 Summary of of 12-Lead ECG, baPWV, ABI, E/E', and HU (Normal/Abnormal) (Safety Population)

Table 14.4.3.3 Transition Table of 12-Lead ECG, baPWV, ABI, E/E', and HU after 12 Weeks (Safety Population)

Table 14.4.4.1 Summary of Laboratory Assessment-Lipid Profile (Safety Population)

Table 14.4.4.2 Summary of Laboratory Assessment-Serum Chemistry (Safety Population)

Table 14.4.4.3 Summary of Laboratory Assessment-Hematology (Safety Population)

Table 14.4.4.4 Summary of Laboratory Assessment-Biomarkers (Safety Population)

Table 14.4.4.5 Summary of Laboratory Assessment-Urinary Exam (Safety Population)

Table 14.4.5.1 Summary of Laboratory Assessment-Lipid Profile (Normal/Abnormal) (Safety Population)

Table 14.4.5.2 Summary of Laboratory Assessment-Serum Chemistry (Normal/Abnormal) (Safety Population)

Table 14.4.5.3 Summary of Laboratory Assessment-Hematology (Normal/Abnormal) (Safety Population)

Table 14.4.5.4 Summary of Laboratory Assessment-Biomarkers (Normal/Abnormal) (Safety Population)

Table 14.4.5.5 Summary of Laboratory Assessment-Urinary Exam (Normal/Abnormal) (Safety Population)

Table 14.4.5.6 Summary of Laboratory Assessment-Microscopy (Normal/Abnormal) (Safety Population)

Table 14.4.6.1 Transition Table of Laboratory Assessment-Lipid Profile (Safety Population)

Table 14.4.6.2 Transition Table of Laboratory Assessment-Serum Chemistry (Safety Population)

Table 14.4.6.3 Transition Table of Laboratory Assessment-Hematology after 12 Weeks (Safety Population)

Table 14.4.6.4 Transition Table of Laboratory Assessment-Biomarkers after 12 Weeks (Safety Population)

Table 14.4.6.5 Transition Table of Laboratory Assessment-Urinary Exam after 12 Weeks (Safety Population)

Table 14.4.6.6 Transition Table of Laboratory Assessment-Microscopy after 12 Weeks (Safety Population)

Table 14.4.7.1 Summary of Subject Compliance for the Study Drugs (Safety Population)

Table 14.4.8.1 Summary of Adverse Events by Treatment Groups (Safety Population)

Table 14.4.8.2 Summary of Adverse Events by MedDRA Coding (Safety Population)

Table 14.4.9.1 Summary of Concomitant Medication by Treatment Groups (Safety Population)

Table 14.4.10.1 Summary of Concomitant Therapies by Treatment Groups (Safety Population)

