6.2.5. Early termination visit /Withdrawal visit

For subjects who prematurely withdraw from treatment, the same procedures as the one at the end of the treatment will be applied. An end of treatment visit should be scheduled as soon as possible and the assessments listed below should be performed. Subjects will be required to bring in all study drugs for assessment of compliance. If the decision of discontinuation is being taken while the subject is in the clinic for a visit, the end of treatment assessments may be performed on that day.

- Physical examination
- Anthropometric measures (Height, weight, waist circumference, BMI)
- Vital signs (pulse rate, body temperature, respiratory rate, and blood pressure)
- Blood samples for
 - lipid profile (total cholesterol, TG, HDL-C, LDL-C and LDL/HDL ratio)
 - hematology (WBC, RBC, Hb, Hct, RDW, platelet, MCV, MCH, MCHC, neutrophil-band and segment, lymphocyte, monocyte, eosinophil, basophil)
 - serum chemistry (AST, ALT, CPK, BUN, serum creatinine, albumin, total bilirubin, direct bilirubin, ALP, total protein)
 - biomarkers (hsCRP, IL-1, IL-6, and TNF-alpha)
- 12-lead electrocardiogram
- Brachial-ankle pulse wave velocity (baPWV) and ankle-brachial index (ABI)
- CT scan of the liver for patients with confirmed fatty liver at Visit 2
- Urinalysis
 - routine urine test (pH, protein, glucose, ketone, blood, urobilinogen, bilirubin, nitrite, leukocyte)
 - clinical microscopy
- Information on adverse events
- Information on new concomitant medications

A safety follow-up should be conducted for subjects who prematurely withdraw from treatment

2 weeks after the end of treatment visit. A clinic visit is recommended unless the subject refused to return. If so, the safety follow-up may be conducted via telephone.

Subjects willing to provide information should be followed for assessments of adverse events until the end of the trial. At a minimum, the investigator should make every effort to obtain information on whether or not the subject is alive or dead at the end of the study.

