9.4. Analysis Plan

General data analysis

For continuous endpoints, descriptive statistics including number, mean, median, standard deviation, minimum, maximum, and 95% confidence intervals will be presented. Continuous variables will be analyzed by means of ANOVA with Bonferroni adjustment. Paired T-Test will be used to compare the change from baseline within treatment groups. If the data strongly indicate a violation of the normal assumption, the non-parametric method of Kruskall Wallis test or Wilcoxon Signed-Rank Test will be applied for analysis.

For categorical endpoints, the count and percentages will be used to summarize the categorical data. The Chi-square test will be performed to test the difference between groups while Fisher's exact test will be applied for any counting of the frequency is less than 5.

All statistical analyses will be conducted using SAS software.

Endpoints

The primary efficacy endpoint for assessing the superiority of Antroquinonol to placebo will be analyzed using analysis of covariance (ANCOVA) model and baseline measurement as covariates, if the differences in baseline characteristics, such as gender, age, weight etc., are observed, for comparing the effectiveness between the treatment groups.

Analysis of other secondary efficacy endpoints (TC, HDL-C, LDL-C, and LDL/HDL ratio as well as the effect of Antroquinonol on E/E', baPWV and ABI and HU parameters) will be similar to the primary analysis of the primary endpoint. All tests will be based on a significance level of 0.05, without adjustment for multiple endpoints.

For the safety assessments, the information of adverse events will be described in detail. Count

and percentage will be tabulated for the number of patients with AEs, number of total AEs, number of patients with AEs associated to study dosing and intensity. Adverse events will be coded by the Medical Dictionary for Regulatory Activities (MedDRA®) adverse event dictionary. All the AEs will be categorized by each represented Preferred Terms (PT) and System Organ Class (SOC), which will be tabulated by body system with related incidence rates. The clinical laboratory tests and electrocardiogram tests will be analyzed to separate subjects into normal and abnormal categories, with number of subjects and percentage of subjects in each category, and McNemar's test or Fisher's exact test will then be applied to test the changes between each visit.

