## 8 SUMMARY OF STUDY DATA

Continuous variables will be summarized by descriptive statistics: number of observations, mean, median, standard deviation, range and 95% C.I. Frequency counts and percentages (based on non-missing sample size) of observed levels will be reported for categorical variables.

Protocol: GHLIP-2-001

Study Sponsor: Golden Biotechnology Corporation

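### Liver HU tables are planned for the whole Safety Population, but only patients with fatty liver at Visit 2 are rescanned, so HU shown by visit compares different patients

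*SAP*

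**What the plan says.** Protocol 7.5.1 sets the schedule: "Each participant will undergo non-enhanced liver computed tomography (CT) scans at visit 2", and then "Subjects who are confirmed with fatty liver will undergo liver CT scans again at visit 5". Fatty liver is defined on that first scan ("L/S ratio <1.0 and liver attenuation <40HU"). Footnote 5 to the SAP flow chart (4.1.1) repeats the restriction: "CT scan will not be scheduled at visit 5 on subjects without fatty liver". Protocol 6.2.5 applies it at early termination too: "CT scan of the liver for patients with confirmed fatty liver at Visit 2".

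SAP 14.4 nevertheless puts HU alongside baPWV, ABI and E/E', which are scheduled for everyone at both visits. It does so in a summary (Table 14.4.3.1), a normal/abnormal table (14.4.3.2) and a transition table: "Table 14.4.3.3 Transition Table of 12-Lead ECG, baPWV, ABI, E/E', and HU after 12 Weeks (Safety Population". SAP 7.4.3 defines the Safety Population as every patient who received study medication. No section limits these tables to rescanned patients, and the SAP does not say what normal or abnormal means for HU.

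Three general rules then apply. SAP 7.3 imputes nothing for secondary or safety analyses. SAP 8 sets the denominator: "Frequency counts and percentages (based on non-missing sample size) of observed levels will be reported for categorical variables". Protocol 9.4 says of continuous variables: "Paired T-Test will be used to compare the change from baseline within treatment groups"; the Protocol Summary and SAP 9.2 say much the same. The section that names HU, SAP 9.4, plans comparisons between arms by ANCOVA with baseline as covariate, or by Kruskal-Wallis.

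**The concern.** The Visit 2 scan is both the selection test and the baseline. Three consequences follow if the tables are produced as titled.

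- **By-visit figures.** Visit 2 describes everyone; Visit 5 describes only those who started low. The mean falls and the abnormal percentage rises with no change in any patient.
- **Transitions.** If abnormal means fatty liver, or simply HU below 40, no patient who was normal at Visit 2 has a second scan. New fatty liver on treatment is not measured, yet the table carries a safety title.
- **Paired change.** Patients enter the paired set because their first reading was low. Part of that is measurement error, so the second reading is higher on average (regression to the mean).

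The by-visit tables would thus point to worsening, while paired changes and transitions would point to improvement, with no drug effect behind either. Fatty liver is a named secondary objective, so these tables are likely to be read.

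**Working it through.** The documents give no HU mean, SD, repeatability, fatty-liver prevalence or HU sample size, so there is no planned figure to reproduce.

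**Inputs from the documents.** Cut-off 40 HU (Protocol 7.5.1); 30 randomized and 24 evaluable patients per arm (SAP 5); two-sided 5% tests (SAP 7.12).

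**Assumptions.** True HU is normal with mean μ = 45 or 50 and SD σ = 12 or 15. Each scan adds independent error with SD e = 3 or 5. There is no true change. Abnormal means HU below 40. The L/S ratio condition is not modelled.

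**Formulas.**
- SD of one reading: s = √(σ² + e²); correlation of two readings: ρ = σ²/s²
- z = (40 − μ)/s; share rescanned: p = Φ(z); λ = φ(z)/p
- By-visit shift (rescanned at Visit 5 minus all at Visit 2): −ρsλ
- Paired change in rescanned patients: (1 − ρ)sλ = (e²/s)λ
- Abnormal at Visit 5: P(both readings < 40)/p, from the bivariate normal

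**One case in full: μ = 50, σ = 12, e = 5.**
- s = √(144 + 25) = 13.0; ρ = 144/169 = 0.852
- z = −10/13 = −0.769; p = 0.221; λ = 1.344
- Shift: −0.852 × 13.0 × 1.344 = −14.9 HU
- Paired change: (25/13) × 1.344 = +2.6 HU
- Abnormal: 22% at Visit 2, 71% at Visit 5
- Rescanned: 24 × 0.221 ≈ 5 per arm

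**All eight cases.** The last column is the simulated rejection rate of a paired t-test with no true change, at the rescanned number shown.

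| μ, σ, e | Abnormal V2 | Abnormal V5 | By-visit shift | Paired change | Rescanned of 24 | Paired t rejects |
|---|---|---|---|---|---|---|
| 45, 12, 3 | 34% | 85% | −12.5 | +0.8 | 8 | 7% |
| 45, 12, 5 | 35% | 77% | −11.7 | +2.0 | 8 | 11% |
| 45, 15, 3 | 37% | 89% | −15.0 | +0.6 | 9 | 6% |
| 45, 15, 5 | 38% | 82% | −14.4 | +1.6 | 9 | 10% |
| 50, 12, 3 | 21% | 81% | −16.0 | +1.0 | 5 | 7% |
| 50, 12, 5 | 22% | 71% | −14.9 | +2.6 | 5 | 10% |
| 50, 15, 3 | 26% | 86% | −18.5 | +0.7 | 6 | 6% |
| 50, 15, 5 | 26% | 78% | −17.6 | +2.0 | 6 | 9% |

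**Different assumptions.** With a mean of 45, 50 or 55, an SD of 10 for a single reading, and correlation between scans of 0.8 to 1.0, the by-visit shift is −9 to −19 HU. At perfect repeatability it is −11.4, −15.2 and −19.4 HU, while the paired change is exactly zero. The by-visit distortion therefore needs no measurement error; the paired one comes only from it.

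**Between arms.** In the second set of assumptions, a null comparison of two arms in rescanned patients rejects in 3.6–5.3% of trials where about 5 to 9 of 30 per arm are rescanned. Selection uses the baseline scan in the same way in every arm, so it does not bias this comparison.

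**The case against.** The strongest reply is that no inferential result is damaged. SAP 9.4 plans HU comparisons between arms, and a percentage change can use only patients with both scans. That stands, and it limits the harm to descriptive HU tables and any within-arm p-values.

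The layout of Tables 14.4.3.1 to 14.4.3.3 is also unknown. No shell is given, and the title of 14.4.3.1 does not say by visit, whereas that of 14.4.1.1 does. A fall in the number of observations would be visible. This too is fair, but the Protocol Summary has continuous variables summarized at each visit, and nothing tells the programmer to treat HU differently.

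A reader might infer more than the documents support:

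- That the SAP specifically plans within-arm tests of HU. It does not. They follow only from general rules that do not name HU, and the McNemar test in SAP 9.5 is stated for laboratory and ECG categories.
- That a false improvement will appear in every arm. It is a bias in expectation. In the eight cases above, with no drug effect, all four arms have a positive mean change in only about 20–41% of trials.
- That the transition table will report zero new cases. Patients normal at Visit 2 have no second scan and nothing is imputed, so that row is unobserved, not a count of zero.

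**Conclusion.** The mismatch is real and nothing in either document corrects it. HU shown by visit for the Safety Population compares different patients, and a false worsening is expected in each arm whatever the repeatability of the scan. New fatty liver cannot be seen if abnormal means fatty liver. If the general paired-test rule is applied to HU, the within-arm change is biased upward on average, by +0.6 to +2.6 HU in the illustration, and the nominal 5% test rejects in about 6–11% of null arms.

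All magnitudes rest on assumed HU values; the direction of the by-visit distortion does not. It would be wrong to conclude that the dose-versus-placebo comparison of HU is compromised: it is small, at about 5 to 9 patients per arm under these assumptions, but not biased by the selection. The primary endpoint is untouched. This should be corrected in the SAP but does not threaten the trial's main conclusion.

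**What to change.** In the SAP:

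1. Define the HU analysis set as patients with fatty liver at Visit 2 and a repeat CT, and report its size per arm and visit.
2. Remove HU from Tables 14.4.3.1 to 14.4.3.3, or restrict both visits in those tables to that set. If they stay, define normal and abnormal for HU by the protocol's fatty-liver definition (both conditions), and mark the normal-to-abnormal cell as not observed. Report the all-patient Visit 2 scan as a baseline description only.
3. Exempt HU from the general within-arm paired tests. Restricting to rescanned patients does not remove regression to the mean, so add a note that abnormal-to-normal transitions include it.
4. Base HU conclusions only on the dose-versus-placebo comparisons in SAP 9.4, within this set.

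The cost is wording in the SAP and table shells, and the loss of within-arm HU p-values. No extra scans are needed.
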